## 8.6.1 Data summaries for ophthalmic evaluations

Summaries on the safety set by treatment group include:

- Summary statistics of visual acuity by visit
- Changes from baseline in visual acuity by visit
- Frequency (%) distribution of categorized visual acuity by visit
- Frequency (%) distribution of categorized change from baseline in visual acuity by visit
- Summary of diagnosis of macular edema

## 8.7 Dermatology assessment

Dermatology examinations will be performed at screening, and Month 12/end of study visits according to a protocol. Results of the dermatology exams are categorical (normal or abnormal with abnormal types) and will be summarized by treatment group for each visit as well as for the unscheduled visit. For unscheduled visit summary, if a subject has 2 or more unscheduled assessments, only the worst result will be summarized.

One shift table from baseline assessment to Month 12/end of treatment assessment will also be presented.

# 8.8 First dose (second dose or restart dose) of fingolimod monitoring

## 8.8.1 Vital signs

Hourly vital signs including pulse, SBP and DBP are collected at pre-dose and 6 hours after the first dose, second dose (if necessary), and restarting of dose after interruption (if applicable). The resting pulse and its change from pre-dose and percent change from pre-dose will also be categorized by pre-specified cutoffs as given in the table shells. The bradycardia events, bradycardia symptoms, and bradycardia treatment during the first dose, second dose (if necessary), and restarting of dose after interruption (if applicable) monitoring will be collected and summarized as well.

The bradycardia events, bradycardia symptoms, and bradycardia treatment will be collected on the corresponding CRFs. Note: Bradycardia events that do not have symptoms or require treatment are not collected in those CRFs and they are recorded in the Adverse Event CRF.

#### 8.8.2 ECG

ECG will be performed at pre-dose and 6 hours post dose during the first dose, second dose (if necessary), and restarting of dose after interruption (if applicable) monitoring.

## 8.8.3 Dose monitoring experience

The overall dose monitoring experience refers to the following information: whether subjects are discharged after 6 hours post-dose or extended monitoring is required after 6 hours post-dose, whether subjects are hospitalized, whether subjects are required monitoring on the next day, whether subjects have symptomatic and/or treated bradycardia, whether subjects discontinue the study drug permanently, whether SAE is reported, and whether subjects are discharged but returned to clinic.

## 8.8.4 Data summaries for first dose monitoring

Summaries on the safety set by treatment group include:

- Summary statistics of vital signs by hour (1st dose, 2nd dose, and restarts)
- Changes from pre-dose in vital signs by hour (1st dose, 2nd dose, and restarts)
- Frequency (%) distribution of categorized supine and standing pulse or change (or percent change) from pre-dose supine and standing pulse during first dose administration, respectively
- Summary of the overall dose monitoring experience (1st dose, 2nd dose, and restarts)
- Incidence rates of bradycardia events (1st dose and 2nd dose)
- Incidence rates of medications used for bradycardia (1st dose and 2nd dose)

- Incidence rates of bradycardia symptoms by SOC, PT, and severity (1st and 2nd dose)
- Incidence rates of notable vital sign abnormalities based on the notable criteria in Table 4-5 (1st dose and 2nd dose)
- Summary statistics of ECG parameters by time point during 1st and 2nd dose administration
- Changes from pre-dose in ECG parameters by time point during 1st and 2nd dose administration
- Incidence rates of abnormal QTc interval (Bazett and Fridericia) as defined by the abnormality criteria in Table 4-6 during 1st and 2nd dose administration
- Frequency (%) distribution of ECGs interpretation (normal/abnormal) by time point during 1st and 2nd dose administration
- Frequency (%) distribution of ECG findings by ECG evaluation type by time point during 1st and 2nd dose administration

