- ECG at 6 hours after dosing should not show any new significant abnormalities (e.g., onset second-degree or third-degree AV block, QTc ≥500 msec) other than sinus bradycardia, that were not also observed at the patient's predose ECG

If the discharge criteria listed above are not met after 6 hours, observation must be continued until symptoms resolve.

If a patient requires treatment for bradycardia/bradyarrhythmia during the first dose observation, the patient should be monitored overnight, and the 6-hour monitoring procedure should be repeated for the second dose of study drug.

If a patient experiences a QTc interval greater than or equal to 500 msec at 6 hours after the first dose, the patient should be monitored overnight, and the 6-hour monitoring procedure should be repeated for the second dose of study drug.

Patients with some pre-existing conditions (e.g., ischemic heart disease, history of myocardial infarction, congestive heart failure, history of cardiac arrest, cerebrovascular disease, uncontrolled hypertension, history of symptomatic bradycardia, history of recurrent syncope, severe untreated sleep apnea, AV block, sinoatrial heart block) may poorly tolerate the fingolimod-induced bradycardia, or experience serious rhythm disturbances after the first dose of fingolimod. Prior to treatment with fingolimod, these patients should have a cardiac evaluation by a physician appropriately trained to conduct such evaluation, and, if treated with fingolimod, should be monitored overnight with continuous ECG in a medical facility after the first dose.

Since initiation of fingolimod treatment results in decreased heart rate and may prolong the QT interval, patients with a prolonged QTc interval (>450 msec males, >470 msec females)

before dosing or during a 6-hour observation period, or at additional risk for QT prolongation (e.g., hypokalemia, hypomagnesemia, congenital long-QT syndrome), or on concurrent therapy with QT-prolonging drugs with a known risk of torsades de pointes (e.g., citalopram, chlorpromazine, haloperidol, methadone, erythromycin) should be monitored overnight with continuous ECG in a medical facility.

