5.5.6 Permitted dose adjustments and interruptions of study treatment

Dose adjustments will not be allowed; however, drug interruptions will be allowed based on the judgment of the investigator. If an investigator determines that study drug should be stopped, then the SC injections or oral capsules, respectively, need to be stopped. Conditions or events that may lead to study drug interruptions based on investigator judgment and overall clinical assessment are:

- SAE
- emergency medical condition or unplanned hospitalization involving the use of prohibited medications (Section 5.5.9)
- abnormal laboratory value(s) or abnormal test or examination result(s) (e.g., ECG values, ophthalmic findings). See Appendix 3 and Appendix 4 for guidance on monitoring of patients with specific test abnormalities
- hypersensitivity to the study drug
- patient noncompliance
- vaccination

The 6-hour monitoring procedure when restarting study drug is mandatory in the following cases:

- the treatment lasted for 14 days or less and was interrupted for 1 day or more, or
- the treatment lasted for more than 14 days and less than 29 days and was interrupted for more than 7 consecutive days, or
- the treatment lasted for 4 weeks or more and was interrupted for more than 14 consecutive days.

Should a patient randomized to one of the fingolimod treatment arms interrupt the study drug as described above and should the investigator decide to reinitiate treatment with the study drug, the first dose intake at restart must take place at the study site to ensure at least 6-hour monitoring by the treating physician in a similar manner as the first intake of the study drug (see for guidelines for monitoring of patients taking their first dose of the study drug in Section 5.5.5).

A reason for the interruption of treatment and dates of interruption should be documented in the source documents as well as in the dosage administration eCRF.

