#### 3.8.4 Time points for first dose monitoring ECG and Vital signs

For the first dose monitoring ECG, data will be summarized for the following time points:

- Day 1 pre-dose: day 1 ECG value at 0 hour per time label
- Day 1 post-dose (6 hours): day 1 ECG value at 6 hours per time label.
- Day 1 post-dose (>6 hours): the mean of all day 1 ECG values after 6 hours per time label (including unscheduled values).

Unscheduled ECG measured between the day 1 pre-dose and the 6 hours post-dose will not be summarized but reported in the data listing only. For the second dose monitoring ECG, data will be summarized similarly.

For the first dose monitoring vital signs, data will be summarized for the following time points:

- Day 1 pre-dose: day 1 vital sign value at 0 hour per time label
- 1 hour post-dose
- 2 hours post-dose
- 3 hours post-dose
- 4 hours post-dose
- 5 hours post-dose
- 6 hours post-dose

The vital sign values at specified hours per time label post-dose will be used. Extended first dose monitoring after the 6 hours post-dose will not be summarized but reported in the data listing only. For the second dose or restart dose monitoring vital signs, data will be summarized similarly.

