#### 8.4.4 Data summaries for ECG data

The following summaries will exclude ECG data from the first dose or second dose or restart dose monitoring.

Summaries on the safety set by treatment group include:

- Summary statistics of quantitative ECG parameters by visit
- Changes from baseline in quantitative ECG parameters by visit
- Incidence rates of abnormal corrected QT interval (Bazett and Fridericia) as defined by the abnormality criteria in Table 4-6
- Frequency (%) distribution of ECGs interpretation (normal/abnormal) by visit
- Frequency (%) distribution of ECG findings by ECG evaluation type by visit

Note: For this study the only post-baseline visit is Month 12/EOT (end of treatment). So, all summaries above will be present for Baseline and then Month 12/EOT.

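### The SAP says restart-dose monitoring data will be summarized, but its listed tables leave restart ECGs out of every ECG summary and drop the restart bradycardia incidence, medication and symptom tables

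*SAP*

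**What the plan says.** Protocol 5.5.6 introduces its list of qualifying interruptions with "The 6-hour monitoring procedure when restarting study drug is mandatory in the following cases", and adds for the fingolimod arms that "the first dose intake at restart must take place at the study site to ensure at least 6-hour monitoring", in a manner similar to the first intake. Protocol 5.5.5 shows which ECG findings matter in that procedure. Its discharge criteria name new significant abnormalities such as "onset second-degree or third-degree AV block, QTc" of 500 msec or more.

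SAP 8.8.2 has ECGs before dosing and at 6 hours for the first dose, "second dose (if necessary), and restarting of dose after interruption (if applicable) monitoring". SAP 8.8.1 covers bradycardia events, symptoms and treatment at the first dose, second dose and restart, ending with "restarting of dose after interruption (if applicable) monitoring will be collected and summarized as well". SAP 3.8.3.2 keeps restart monitoring data out of the visit windows and says they will be summarized separately.

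Three other places narrow the scope:

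- SAP 8.4.4, for the regular ECG tables: "The following summaries will exclude ECG data from the first dose or second dose or restart dose monitoring".
- SAP 3.8.4, for the monitoring ECG time points: "For the second dose monitoring ECG, data will be summarized similarly". The parallel sentence for vital signs names restart as well as the second dose.
- SAP 8.8.4, for the monitoring outputs: for example "Incidence rates of bradycardia symptoms by SOC, PT, and severity (1st and 2nd dose".

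**The concern.** The SAP promises a restart summary in two places and then lists outputs that do not contain most of it. A programmer working from 8.8.4 would produce no restart ECG table and no restart table of bradycardia events, medications or symptoms. A programmer working from 8.8.1 and 3.8.3.2 would expect them.

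Protocol 1.1 names transient bradycardia after the first dose and AV conduction delay at initiation as fingolimod effects, and says the bradycardia appeared to show a dose response. Protocol 5.5.6 treats a restart after a qualifying interruption as a repeat of the first-dose procedure. Safety in each dose group is a secondary objective (Protocol 2.2). What is at stake is whether the report tabulates, by dose, the ECG and bradycardia findings from a monitoring procedure that the protocol makes mandatory.

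**Working it through.** The plan states no figure to reproduce here. The check traces restart data through the SAP and counts the listed outputs by scope.

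**Step 1. Scope of the 13 outputs in SAP 8.8.4**

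| Output | Number | Doses covered |
|---|---|---|
| Hourly vital signs; change from pre-dose; overall monitoring experience | 3 | First, second, restarts |
| Categorized pulse | 1 | First only |
| Bradycardia events; medications; symptoms | 3 | First and second |
| Notable vital signs | 1 | First and second |
| ECG statistics; change; abnormal QTc; interpretation; findings | 5 | First and second |

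Check: 3 + 1 + 3 + 1 + 5 = 13. Outputs limited to first and second dose: 3 + 1 + 5 = 9. Three entries in the same list name restarts, so leaving them out of the other nine reads as a limit of scope.

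**Step 2. ECG tables that contain restart data**

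- SAP 8.4.4 lists five regular ECG summaries, and restart data are excluded from all of them: 0 of 5.
- SAP 8.8.4 lists five monitoring ECG summaries: 0 of 5.
- Total: 0 of 10.

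SAP 3.8.4 agrees with this outcome, because its ECG time points extend only to the second dose. SAP 3.8.3.2 does not agree. It names ECG among the data with visit windows and then promises a separate summary of restart monitoring data.

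**Step 3. Where restart findings can still appear**

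- Listings: SAP 8 lists all safety data.
- AE tables: Protocol 6.5.4 sends only clinically significant ECG abnormalities to the AE form, and SAP 8.8.1 sends bradycardia without symptoms or treatment there. The AE summaries in SAP 8.1.3 are not split by restart.
- Monitoring-experience table: SAP 8.8.3 includes items on symptomatic and/or treated bradycardia, extended monitoring and next-day monitoring. This table covers restarts but does not give the ECG reason.
- Hourly vital signs at restart.

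Of the three dedicated bradycardia tables, 0 of 3 cover restarts.

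**Step 4. Rough scale**

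SAP 10 gives 370 and 352 patients randomized to the two fingolimod arms: 370 + 352 = 722. The documents do not give the number of restarts. Assume that 2% to 5% of these patients have a monitored restart:

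- 0.02 × 722 = 14.4, about 14 patients.
- 0.05 × 722 = 36.1, about 36 patients.

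Protocol 1.1 puts second-degree AV block below 0.5% of patients on 0.5 mg. If that ceiling is applied to restarts in both arms (a further assumption), the expected number is below 0.005 × 14.4 = 0.07 to 0.005 × 36.1 = 0.18, so below about 0.2 in total.

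**The case against.** The strongest reply is that little is actually hidden.

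- *Restart bradycardia is summarized.* The monitoring-experience table covers restarts and has a symptomatic-or-treated item, which matches what the bradycardia forms collect. The remainder goes to the AE form. This stands: a reader might infer that restart bradycardia is unreported, and the SAP does not support that. What is missing is event incidence, the breakdown of symptoms by system organ class, preferred term and severity, and the medications used.
- *Serious ECG findings do not sit only in a listing.* New second- or third-degree AV block, or QTc of 500 msec or more, fails the discharge criteria. Such a patient should count under extended monitoring in the restart table, and a clinically significant finding should be an AE. This largely stands. Neither route identifies the finding as an ECG abnormality at restart.
- *The list is not closed.* SAP 8.8.4 says that summaries include those listed, and the full output list is in RAP Module 7.1, which is not among the documents. The shells may therefore contain restart tables. This limits the claim to the outputs as listed. It does not remove the conflict between explicit dose limits in 8.8.4 and the promises in 3.8.3.2 and 8.8.1.
- *The split may be deliberate.* SAP 3.8.4 draws the same line, with vital signs extended to restart and ECG not. Listing sparse ECGs taken after interruptions of varying length is defensible. If that was the choice, the SAP does not say so, and 3.8.3.2 says otherwise.
- *No dose comparison is lost.* A reader might infer that the omission is what prevents comparing 0.25 mg with 0.5 mg on conduction findings at restart. With fewer than about 0.2 second-degree blocks expected under the assumptions above, no table would support that comparison. This stands in full.

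**Conclusion.** The inconsistency is real and minor. As listed, restart ECGs enter 0 of 10 ECG tables and restart bradycardia enters 0 of 3 dedicated tables, although SAP 3.8.3.2 and 8.8.1 say these data will be summarized. The notable vital-sign table has the same gap.

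The data are not lost, and bradycardia at restart is not wholly unsummarized. The gap is the absence of a descriptive table, by dose, of QTc, conduction and bradycardia findings identified as restart findings. No endpoint, test or power figure depends on it.

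The conclusion rests on the SAP text alone, since the table shells were not available. The figure of 14 to 36 patients rests on an assumed restart fraction with no source in the documents, and serves only to show that numbers will be small.

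**What to change.** Reconcile SAP 8.8.4 and 3.8.4 with 3.8.3.2, 8.8.1 and 8.8.2:

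1. In 8.8.4, extend the five ECG outputs, the three bradycardia outputs and the notable vital-sign output to restarts, shown as a separate descriptive block by dose.
2. Use each restart's own pre-dose value as the reference for change.
3. State the counting rule: incidence is per patient with at least one monitored restart, the worst restart counts, and the number of restarts is shown. A rule is needed because SAP 3.8.6 exempts restart monitoring data from its multiple-assessment rules.
4. In 3.8.4, add restart dose to the sentence that extends the ECG time points to the second dose.

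The cost is a wording change and a re-run of existing table programs on data already collected. No new assessment is needed, and no dose, monitoring or stopping rule changes. The downside is sparse cells, so the block should be labelled descriptive.

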## 8.9 Columbia Suicide Severity Rating Scale (C-SSRS)

#### General

The Columbia Suicide Severity Rating Scale (C-SSRS) is a questionnaire that prospectively assesses suicidal ideation and behavior (SIB). There are two versions of the questionnaire:

- The "baseline/screening" version, which is to be performed at the first visit (Visit 1). It assesses SIB during the subject's lifetime.
- The "since last visit" version to be used at subsequent visits (Visit 2 to Visit 7), assessing SIB since last visit.

A copy of the questionnaires can be found in protocol amendment Appendix or CRF package.

The 11 categories described in Table 7-1 have been adopted as standard by FDA to report SIB ([Food and Drug Administration, 2012], [Nilsson et al, 2013]). These categories include five levels of suicidal ideation, five levels of suicidal behavior and the category self-injurious behavior, no suicidal intent. Each category has a binary response (yes/no). The C-SSRS questionnaire allows suicidal ideation and behavior to be classified into these 11 preferred categories.

Note: the categories in Table 7-1 have been reordered (based on [Nilsson et al 2013]) compared to the categories in the actual C-SSRS (paper) scale and the categories listed in the FDA guidance, in order to facilitate the definitions of endpoints and enable clarity in the presentation of results.

Table 7-1 Standard SIB events

Category number	C-SSRS category
Suicidal Ideation	

Protocol No. CFTY720D2312

RAP Module 3

Category number	C-SSRS category	
1	Wish to be dead	
2	Non-specific active suicidal thoughts	
3	Active suicidal ideation with any methods (not plan) without intent to act	
4	Active suicidal ideation with some intent to act, without specific plan	
5	Active suicidal ideation with specific plan and intent	
Suicidal behav	vior	
6	Preparatory acts or behavior	
7	Aborted attempt	
8	Interrupted attempt	
9	Actual attempt	
10	Completed suicide	
Self-injurious	behavior, without suicidal intent	
11	Non-suicidal self-injurious behavior	

In this study, the C-SSRS questionnaire will be administered electronically (eC-SSRS), via an interactive voice response (IVR) system with the patient entering responses directly into the IVRS. Caregivers will not be allowed to answer the C-SSRS questions on behalf of the patient. Sites must review reports received from the system for any answers indicative of suicidal ideation and adverse event AEs. Adverse events ascertained through the administration of the C-SSRS will be documented. No safety cut-off will be applied for the SIB data reporting, i.e. all collected data will be used in the analysis including data collected off-treatment, if any.

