A dermatologist will complete a dermatological examination as outlined in Table 6-1 and Table 6-2 to support monitoring of patients for the potential development of new skin cancers during the study. For patients who discontinue treatment early, a dermatological examination should be performed at end of study. Study drug should be discontinued in patients who develop a new skin cancer during the study.

6.5.11 **Columbia-Suicide Severity Rating Scale**

The C-SSRS, is a semi-structured interview designed to systematically assess and track suicidal AEs (behavior and ideation) throughout different settings including clinical studies.

The C-SSRS captures the occurrence, severity, and frequency of suicide-related thoughts and behaviors. The C-SSRS will be administered by an IVRS with the patient entering responses directly into the IVRS. Caregivers will not be allowed to answer the C-SSRS questions on behalf of the patient. Sites must review reports received from the system for any answers indicative of suicidal ideation and AEs. Adverse events ascertained through the administration of the C-SSRS will be documented. This scale was developed by researchers at Columbia University and will be administered in this study as specified in the assessment schedules

(Table 6-1 and Table 6-2). In case the score is 4 or above, the patient must be referred to the health care professional for further assessment and/or treatment.

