## Definition of 'all prior history'

All prior history will be defined as the SIB results obtained from the *lifetime* assessment at the first visit (Visit 1).

Worst case is defined by an answer 'yes' to the SIB category.

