## Data summaries at the study level

SIB data will be summarized for the Safety Set. The number and percentage of subjects with suicidal ideation, suicidal behavior and self-injurious behavior without suicidal intent will be presented by analysis-period (all prior history and any time post-baseline) and treatment group. The following 14 events will be included in the summary table:

- Each of the 11 categories listed in Table 7-1, separately
- Any suicidal ideation or behavior (a 'yes' answer to at least one of the 10 suicidal ideation and behavior questions in analysis-period of interest)
- Any suicidal ideation (answered 'yes' to at least one of the 5 suicidal ideation questions in analysis-period of interest)

Protocol No. CFTY720D2312

 Any suicidal behavior (answered 'yes' to at least one of the 5 suicidal behavior questions in analysis-period of interest).

For those analyses, each subject can only be counted once for each event. However, a subject can be counted in several different events.

Suicidal ideation and behavior data will be listed. Detailed answers to C-SSRS items will be listed separately for subjects with any suicidal ideation at any time post-baseline (i.e. a 'yes' answer to at least one of the five suicidal ideation questions at any time post-baseline) and for subjects with any suicidal behavior at any time post-baseline (i.e. a 'yes' answer to at least one of the five suicidal behavior questions at any time post-baseline).

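### SAP 8.9 fills the completed-suicide row of the C-SSRS table only from answers the patient enters by telephone, so its post-baseline count is zero by rule

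*SAP*

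**What the plan says.** SAP 8.9 (General, Table 7-1) sorts suicidal ideation and behavior into eleven yes/no categories: five of ideation (1 to 5), five of behavior (6 to 10) and one of self-injury without suicidal intent (11). Category 10 is "Completed suicide".

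Under its heading on study-level summaries, the SAP says: "The following 14 events will be included in the summary table". The first item is "Each of the 11 categories listed in Table 7-1, separately"; the other three are composites. The behavior composite requires that the patient "answered 'yes' to at least one of the 5 suicidal behavior questions", and the combined ideation-or-behavior composite uses all ten ideation and behavior questions in the same way. The listing of patients with post-baseline suicidal behavior uses the same criterion. A separate line adds: "Worst case is defined by an answer 'yes' to the SIB category".

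On the source of the answers, SAP 8.9 describes electronic administration "with the patient entering responses directly into the IVRS. Caregivers will not be allowed to answer the C-SSRS questions on behalf of the patient". Protocol 6.5.11 agrees: "The C-SSRS will be administered by an IVRS with the patient entering responses directly into the IVRS".

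The adverse event plan is separate. SAP 8.1.2 counts deaths as SAEs and includes every SAE that starts after the first dose, even more than 45 days after the drug is stopped. SAP 8.1.3 lists deaths and SAEs by system organ class and preferred term.

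**The concern.** A completed suicide is the one category that the person concerned can never report. If the table accepts only that person's own answers, the row carries no information about what happened in the trial, yet it would be printed beside rows that do.

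A reader of a standard eleven-category table will take a zero in that row as an observed result. If a suicide did occur, the same report could show it in the deaths table and show none in the suicidality table, with nothing to explain the difference. Amendment 1 of the protocol added the suicidality assessment to follow FDA guidance, so this is a table that will be read closely.

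**Working it through.** No script was needed. The check is a count of the rows, followed by a comparison of what each row needs with what the stated source can supply.

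**Step 1: reproduce the SAP's row count.** 5 ideation + 5 behavior + 1 self-injury = 11 categories. 11 + 3 composites = 14 rows, as stated. The combined composite uses 5 + 5 = 10 questions, also as stated.

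**Step 2: can category 10 ever be yes?**
- Needed: a yes answer (SAP 8.9, the worst-case rule and the study-level summaries).
- Available: the patient's own entry, with caregivers barred from answering (SAP 8.9; the same in Protocol 6.5.11).
- After death: the patient counts as withdrawn (Protocol 5.5.10), so no further entry is made.

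No route to a yes remains, and the row is 0 in every arm. In the column for prior history this is harmless, because everyone who completes screening is alive. The problem is the post-baseline column.

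**Step 3: effect on the composites.** Any suicidal behavior rests in practice on 5 − 1 = 4 categories (6 to 9), and the combined composite on 10 − 1 = 9.
- Undercount in any suicidal behavior = suicides with no earlier post-baseline yes on categories 6 to 9.
- Undercount in the combined composite = suicides with no earlier post-baseline yes on categories 1 to 9.
- The behavior listing misses the same patients as the first composite.

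**Step 4: does another rule fill the gap?** SAP 8.9 applies no safety cut-off to these data. That widens the time span but adds no source. The only stated link to adverse events runs outward: events found through the questionnaire are to be documented. No sentence brings AE, SAE or death records back into the table.

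**Step 5: size.** The documents give no number of suicides, so the undercount cannot be computed. For scale only, assume one suicide and use the final randomized numbers in SAP 10 as approximate denominators (the table itself is on the Safety Set):
- fingolimod 0.25 mg: 1/370 = 0.27%
- fingolimod 0.5 mg: 1/352 = 0.28%
- glatiramer acetate: 1/342 = 0.29%

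Each would be printed as 0.0% in this row. With no suicide, the table is the same under either rule.

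**The case against.** The strongest reply is that the table does what the protocol asks. Protocol 9.5.2 calls for a frequency distribution taken from the C-SSRS, so this is a summary of an instrument. Two tables from different sources need not agree, and the row follows a display that the SAP describes as an FDA standard. The questionnaire copy and the table shells (RAP Module 7.1) are not among the documents, so a rule for category 10 may exist there.

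Part of this stands. The zero is established for the text of the SAP and protocol, not for the finished output. But an instrument summary does not need a row the instrument cannot fill, and nothing in either document tells the reader that the row is uninformative.

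Three stronger readings are tempting and are not supported:
- **A suicide would be lost from the report.** It would not. The deaths and SAE tables in SAP 8.1.2 to 8.1.3 capture it by treatment group.
- **The composites always miss a suicide.** They miss it only when there was no earlier qualifying yes after baseline.
- **Non-fatal attempts are missed in the same way.** Stopping study drug is not withdrawal (Protocol 5.5.10), and Table 6-2 keeps the C-SSRS at Months 6, 9 and 12 off treatment. The follow-up version asks about the time since the last visit, and off-treatment data are used. Only a patient who makes no further call is missed. That is ordinary missing data, not a zero by rule.

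It also stands that adding coded attempts from the AE record to the composites would alter the C-SSRS-based summary the protocol specifies. That is a debatable choice and is not proposed here.

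**Conclusion.** The point holds, at minor severity. Under the SAP as written, the post-baseline completed-suicide row is 0 in every arm regardless of events, and two composites and one listing omit any suicide not preceded by a qualifying yes. The C-SSRS table could then disagree with the deaths and SAE tables without explanation.

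This rests on two assumptions: that patient entry is the only source feeding the table, as both documents state, and that no unseen shell or form supplies another rule. The percentages under one suicide are an illustration, not an estimate. A reader might infer that a single case would dominate the between-arm difference in suicidal behavior, but the documents give no event counts to support that, and SAP 8.9 specifies no test for this table. The primary analysis is unaffected.

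**What to change.** In SAP 8.9, state that post-baseline category 10 is derived from death or SAE records coded as completed suicide. State also that a patient so identified counts in any suicidal behavior, in any suicidal ideation or behavior, and in the behavior listing. Add a footnote naming the source. All other rows stay as answered by the patient.

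There is a precedent in the same SAP: section 8.8.1 notes that bradycardia events outside the dedicated forms are recorded on the Adverse Event CRF, and the document history says they will be identified from there.

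The minimum alternative is a footnote saying that category 10 cannot be observed through patient entry and referring to the deaths table.

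The cost is a few lines of programming on data already collected. The downside is that one row, and its part of the composites, draws on a second source, which the footnote discloses. The row will be as complete as SAE collection: under Protocol 7.2, events more than 30 days after the end of participation are reported only if the investigator suspects a causal relationship to study drug.
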